Protocol Synopsis

Modulation of GABA-A Receptors in Parkinson Disease-Flumazenil Arm

NCT03462641

12/14/2020

Axial motor impairments represent a significant cause of disability in Parkinson disease (PD), which is mainly explained by a lack of efficacy of dopaminergic treatments of these symptoms. Treatment approaches to reduce balance problems and falls have been recently identified as the number 1 research priority in PD. Postural instability and gait difficulties (PIGD) motor features are mediated by widespread neural networks that extend well beyond the nigrostriatal system. There is increasing interest in dysfunction of non-dopaminergic neurotransmitters to better understand the complexity of the multisystem nature of mobility impairments in PD. Flumazenil is a short-acting intravenously administered modulator of the γ -aminobutyric acid-A (GABA-A) receptor benzodiazepine binding site, which has shown to rapidly improve motor impairments in PD. Based upon current basal ganglion models in PD, flumazenil could normalize neuronal signaling of hyperGABA-ergic activity in PD.

We have preliminary data that reduced cerebral GABAA receptor availability (likely reflecting increased synaptic or extracellular GABA-ergic activity) as determined by [^{11}C]flumazenil PET imaging has most robust association with axial compared to other cardinal motor impairments in PD. Although flumazenil therapy has been shown to improve motor symptoms in PD, its practical limitation is that it can only be effectively and reliably given intravenously. The overarching goal of this project is to perform biomechanistic GABAA receptor target engagement studies to investigate the effects of GABAA receptor modulation to motor impairments in PD, including PIGD features using i.v. flumazenil vs placebo in a cross-over study design to be correlated to pretreatment C11-flumazenil PET thalamic binding. Our main hypothesis is that negative allosteric modulation of cerebral GABAA receptor activity improves dopamine-resistant PIGD features.

Statistical Analysis Plan

Modulation of GABA-A Receptors in Parkinson Disease-Flumazenil Arm

NCT03462641

05/31/2022

In this proposal, the investigators present data suggesting that flumazenil (FMZ) administration leads to a decrease in postural instability and gait disorder (PIGD) symptoms of Parkinson's Disease (PD). Further association is made between treatment effectiveness and GABA-A receptor FMZ PET thalamic binding at baseline.

Study participants were pseudo-randomly assigned into A and B sequences, and came in for two visits, with sequence A participants receiving FMZ infusion on the first visit and sequence B participants receiving saline infusion (placebo) on the first visit. The other treatment was given on the subsequent day for participants in both sequences. Detailed motor examination including modified UPDRS was conducted on both days prior to infusion and at 60-90 minutes postinjection. UPDRS PIGD motor subscale score was computed as our primary outcome measure. FMZ PET imaging was done to collect data for the test of interaction between treatment and GABA-A receptor availability.

A paired samples t-test was conducted for each participant's pre and post infusion PIGD score for the flumazenil pharmacological injection treatment only to test whether FMZ pharmacological injection appears to have any effect on PIGD score in a univariate comparison. A repeated measures ANOVA model was used to test the significance of interaction between treatment (FMZ pharmacological injection vs. placebo) and time of administration (pre-infusion vs. post-infusion), with additional three-way interaction term between treatment, time of administration, and sequence (A vs B) included to account for potential confounding effect of sequence. Lastly, a mixed linear model comparison was conducted between the random intercept model and FMZ PET by treatment interaction model, to test the hypothesis that the effect of flumazenil pharmacological i.v. treatment on change in PIGD scores depends on baseline GABA-A FMZ PET receptor availability in the thalamus. Bilaterally averaged thalamic FMZ PET distribution volume ratio (DVR) by treatment (FMZ pharmacological therapy injection vs placebo) was used for the interaction term, and difference between PIGD scores (post – pre) infusion were used as a response variable for that model.

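### The SAP puts the drug-effect question on the primary outcome to a flumazenil-only pre/post t-test, which cannot answer it; the placebo-controlled contrast already in the SAP should carry any such claim

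*SAP*

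**What the plan says.** The Protocol Synopsis sets out to study receptor modulation "using i.v. flumazenil vs placebo in a cross-over study design". The SAP's second paragraph names the outcome: "UPDRS PIGD motor subscale score was computed as our primary outcome measure". The same paragraph gives the measurement schedule: "Detailed motor examination including modified UPDRS was conducted on both days prior to infusion and at 60-90 minutes postinjection". By design, each participant therefore has a pre/post pair for flumazenil and another for saline.

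The SAP's third paragraph lists three analyses:

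1. A paired t-test on each participant's "pre and post infusion PIGD score for the flumazenil pharmacological injection treatment only", done "to test whether FMZ pharmacological injection appears to have any effect on PIGD score in a univariate comparison".
2. The placebo-controlled test: "A repeated measures ANOVA model was used to test the significance of interaction between treatment (FMZ pharmacological injection vs. placebo) and time of administration". A three-way term with sequence is added.
3. A mixed-model comparison asking whether the treatment effect on the change in PIGD depends on thalamic PET binding.

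Neither document labels any of the three as primary, supportive or exploratory. Neither gives a significance level, a testing order, or a rule for the case where the first two analyses disagree. The SAP's opening paragraph says that the investigators "present data suggesting that flumazenil (FMZ) administration leads to a decrease in postural instability and gait disorder (PIGD) symptoms", without tying that statement to a particular test.

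**The concern.** A pre/post change on the flumazenil visit contains the drug effect plus anything else that moves the score between the pre-infusion examination and the one 60 to 90 minutes later. Expectation, repeat testing and time of day are candidates. The documents do not say whether any of them operates here. The t-test counts all of it as drug effect, so it does not answer the question it is given. A placebo cross-over is designed to remove this ambiguity, and the t-test leaves out the half of the data that would do so.

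A second issue arises even if nothing shifts after saline. The t-test and the ANOVA interaction both address whether flumazenil changes the same primary outcome. If either may support a claim, there are two chances of a false positive, and the SAP does not exclude that use.

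**Working it through.** The documents state no error rate, sample size, SD or significance level, so there is no figure to reproduce. The check has two parts: what each test estimates, and an illustration of error rates on assumed inputs.

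**What each test estimates.** Let F be a participant's post-minus-pre change with flumazenil and S the change with saline. Let δ be the drug effect, and let s_F and s_S be the non-drug shifts on the two visits.

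- Flumazenil-only t-test: E(F) = δ + s_F.
- Treatment-by-time contrast: E(F − S) = δ + (s_F − s_S).

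The t-test is a test of δ only if s_F = 0. The contrast needs only s_F = s_S. If the shifts differ between infusions, the contrast does not remove the difference.

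**Assumed inputs, none from the documents.** Two-sided 5% tests; n = 10, 20 or 30, split equally between sequences; normal change scores with SD 1; no visit effect; δ = 0; s_F = s_S = d, with d = 0, 0.1 or 0.3 SD of the change score; correlation ρ between F and S of 0, 0.3 or 0.6.

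**T-test alone.** The rejection probability is P(|T| > t(0.975, n − 1)), where T is noncentral t with n − 1 df and noncentrality d√n. For d = 0.3 the noncentrality is 0.3 × √10 = 0.95, 0.3 × √20 = 1.34 and 0.3 × √30 = 1.64. The probabilities are 0.136, 0.247 and 0.356.

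**Contrast alone.** F − S is averaged within each sequence, the two sequence means are averaged equally, and the result is tested on n − 2 df. Simulation with 200,000 trials per setting gave 0.049 to 0.050 throughout, as expected, because d cancels.

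**Either or both tests.** The tests are correlated because both use F. With equal variances, corr(F, F − S) = (1 − ρ)/√(2(1 − ρ)) = √((1 − ρ)/2), which is 0.71 at ρ = 0 and 0.45 at ρ = 0.6. The either-test rate with no shift should therefore fall below the independent-test value of 1 − 0.95² = 0.0975, and it does.

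False-positive rates with zero drug effect (ranges are over ρ):

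| d | n | t-test alone | Either test | Both required |
|---|---|---|---|---|
| 0 | 10 | 0.050 | 0.086–0.094 | 0.007–0.015 |
| 0 | 20 | 0.050 | 0.085–0.093 | 0.007–0.016 |
| 0 | 30 | 0.050 | 0.084–0.092 | 0.008–0.016 |
| 0.1 | 10 | 0.059 | 0.095–0.102 | 0.007–0.015 |
| 0.1 | 20 | 0.071 | 0.105–0.112 | 0.008–0.017 |
| 0.1 | 30 | 0.083 | 0.116–0.122 | 0.009–0.018 |
| 0.3 | 10 | 0.136 | 0.168–0.174 | 0.011–0.019 |
| 0.3 | 20 | 0.247 | 0.274–0.279 | 0.017–0.023 |
| 0.3 | 30 | 0.356 | 0.382–0.384 | 0.021–0.024 |

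The rate rises above 5% only under rules that let a significant t-test support the claim without the contrast.

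**The case against.** The strongest reply is that the SAP already contains the right analysis. The sentence after the t-test gives the flumazenil-versus-placebo test with a sequence term, the PET model also compares treatment with placebo, and the Protocol Synopsis frames the whole project as a placebo cross-over. The t-test is worded cautiously, and a simple first look followed by a controlled model is a natural reading. All of this stands and limits the point. It does not remove it: the hedge sets no order between the tests, and the t-test's stated purpose is still to detect a drug effect.

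A reader might infer that the t-test is the primary analysis, or that the SAP's opening statement about reduced PIGD symptoms rests on it. The documents support neither. The t-test is not called primary, and the opening sentence is a summary that names no test, so its silence about the ANOVA is not evidence that the t-test was used.

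The larger error rates need an assumed shift with no source in the documents. At d = 0.1 the t-test alone is at 6% to 8%, and at d = 0 it is at 5%. The table shows what a decision rule would allow, not what happened in this trial.

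The contrast has limits too. Expectation cancels only if it is equal under both infusions. The available text does not describe blinding, and it calls the assignment pseudo-random. The contrast's rate of about 5% follows from the equal-shift assumption and is not established for this trial.

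Finally, replacing the p-value with a 95% interval does not by itself help: the interval for the flumazenil change excludes zero exactly when the paired t-test is significant at 5%. The correction must concern what the figure may be used for.

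**Conclusion.** The point holds in a limited form. A stated analysis of the primary outcome does not answer its stated question, because it cannot distinguish flumazenil from whatever also follows saline, and the saline data needed were part of the design. No comparison is missing from the SAP.

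Used as a second efficacy test beside the ANOVA, the t-test raises the false-positive rate to about 8% to 9% with no shift at all, if either result may be claimed. That rests on assumed n of 10 to 30, two-sided 5% tests and correlations of 0 to 0.6. With an assumed shared shift of 0.3 SD the either-test rate is 17% to 38%. If the contrast alone decides, the rate stays at about 5% under equal shifts. A reader might conclude that this trial's error rate was in fact inflated. The documents do not support that, since they neither state nor exclude a rule letting the t-test stand alone.

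This should be fixed, because it governs which evidence may support an efficacy statement. It is not more serious than that, because the controlled test is already there.

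**What to change.** - Remove the flumazenil-only t-test as a test of drug effect.
- State that any claim that flumazenil changes PIGD, including the SAP's opening sentence, rests on the treatment-by-time contrast averaged over the two sequences.
- Report the mean pre/post change with its 95% interval for flumazenil and for saline side by side, as description only. Say explicitly that a flumazenil interval excluding zero is not evidence of a drug effect.
- Note that the contrast removes only shifts that are equal under both infusions.
- Disclose that the designation was made after the analysis, since the SAP reports the analyses in the past tense.

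The cost is a few sentences and one saline mean with its interval, from examinations the SAP says were done; no new model is needed. There are two downsides. The flumazenil-only p-value is lost as evidence. The designation is post hoc, so it clarifies interpretation but cannot be presented as prespecified and cannot restore prespecified error control.

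### The SAP does not say whether the reference model in the PET-moderation comparison holds the treatment and DVR main effects; on its most natural reading, a uniform treatment effect can pass for PET dependence

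*SAP*

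**What the plan says.** The SAP's opening paragraph makes two claims. The first is that there are "data suggesting that flumazenil (FMZ) administration leads to a decrease in postural instability and gait disorder (PIGD) symptoms". The second is about moderation: "Further association is made between treatment effectiveness and GABA-A receptor FMZ PET thalamic binding at baseline". The Protocol Synopsis sets the same aim, motor effects "using i.v. flumazenil vs placebo in a cross-over study design to be correlated to pretreatment C11-flumazenil PET thalamic binding".

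The design paragraph gives the purpose of the imaging: "FMZ PET imaging was done to collect data for the test of interaction between treatment and GABA-A receptor availability".

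The last part of the analysis paragraph describes the test of the second claim. The hypothesis is that the effect of flumazenil "treatment on change in PIGD scores depends on baseline GABA-A FMZ PET receptor availability in the thalamus". The method is that "a mixed linear model comparison was conducted between the random intercept model and FMZ PET by treatment interaction model". Thalamic DVR, averaged over the two sides, "by treatment (FMZ pharmacological therapy injection vs placebo) was used for the interaction term", and the response is the post-minus-pre change in PIGD score.

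Neither model is written out. The product of DVR and treatment is the only fixed term named. The text does not say whether the reference model holds treatment or DVR, whether DVR was centred, which test was used, or on how many degrees of freedom. For the repeated measures ANOVA the SAP specifies a "three-way interaction term between treatment, time of administration, and sequence (A vs B) included to account for potential confounding effect of sequence"; for the mixed model it says nothing about sequence or period.

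**The concern.** A comparison of nested models tests every term by which they differ. The moderation hypothesis concerns one term, DVR x treatment. If the reference is intercept-only, the comparison also tests the treatment main effect and, where the larger model contains it, the DVR main effect. A significant result then need not mean that the treatment effect varies with DVR.

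The confusion is likely to matter here. The response is the change score, so the treatment main effect in this model is the very benefit that the SAP's opening paragraph says the data suggest. The investigators expect that effect to be present. Of the analyses in the SAP, only this comparison addresses the link to PET binding, so the second claim depends on it. The paired t-test and the repeated measures ANOVA are not affected.

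**Working it through.** **Models.** Let y be the PIGD change for participant i on one treatment day, T the treatment, x the participant's DVR, u the random intercept and e the residual:

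y = b0 + b1·T + b2·x + b3·T·x + u + e

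With T coded 0/1, the treatment effect at DVR = x is b1 + b3·x. The hypothesis in the SAP is about b3 alone. A uniform benefit means b1 ≠ 0 and b3 = 0.

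**What each possible pair of models tests.**

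1. Reference intercept-only; larger model T + x + T·x. Tests b1 = b2 = b3 = 0 (3 df). A uniform treatment effect or a DVR main effect makes this null false.
2. Reference intercept-only; larger model adds only T·x (1 df). The flumazenil-minus-saline difference is then modelled as b3·x with no constant. The share of a constant effect's sum of squares that this line absorbs is (Σx)²/(n·Σx²) = 1/(1 + CV²). At CV 15% that is 1/1.0225 = 0.978, so uncentred DVR lets the product stand in for treatment. With mean-centred DVR, Σx = 0 and the share is 0.
3. Reference T; larger model T + x + T·x. Tests b2 = b3 = 0 (2 df). A uniform treatment effect cannot contaminate it; a DVR main effect can.
4. Reference T + x; larger model adds T·x. Tests b3 = 0 (1 df). This is the intended test.

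**Size.** The documents state no figure to reproduce: no n, effect size, SD, correlation, DVR spread or test. The inputs below are all assumptions: n = 20, intraclass correlation (ICC) 0.2, DVR CV 15%, true b3 = 0, no DVR main effect, maximum-likelihood fits, nominal 5%. Effects are in SDs of the within-person flumazenil-minus-saline difference, which is √(2(1 − 0.2)) = 1.265 times the SD of one change score. Simulated rates of declaring PET dependence:

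| Comparison | No effect | 0.5 SD | 0.8 SD |
|---|---|---|---|
| 1, likelihood ratio, 3 df | 7.5% | 45% | 85% |
| 1, cut-off recalibrated to 5% under no effect | 5% | 38% | 80% |
| 1, chosen by AIC | 15% | 61% | 93% |
| 2, uncentred DVR, likelihood ratio | 6% | 59% | 93% |
| 2, centred DVR, likelihood ratio | about 6% | 5% or less | 5% or less |
| 3, likelihood ratio, 2 df | about 7% | about 7% | about 7% |
| 4, likelihood ratio, 1 df | about 7% | about 7% | about 7% |
| 4, t-test of b3 | 5% | 5% | 5% |

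The recalibrated row removes the small-sample bias of the likelihood-ratio test, so what remains above 5% comes from the choice of reference alone. The excess over 5% in the likelihood-ratio rows for comparisons 3 and 4 is that same bias; for comparison 4 it is about 9% at n = 10.

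**Sensitivity.** Comparison 1, recalibrated, at n = 10 / 20 / 30:

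- 0.3 SD: 9 / 16 / 23%
- 0.5 SD: 18 / 38 / 57%
- 0.8 SD: 42 / 80 / 95%

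If 0.5 and 0.8 SD are instead in units of a single change score, the 3-df likelihood-ratio rates at n = 20 are 31% and 65%. A separate simulation with ICC 0.3 and 0.6 and DVR CV 10% gives 44–45% and 83–84% on the within-person scale, so those two inputs matter little. Sample size and effect size matter a good deal.

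**The case against.** The best defence is that a random intercept model is named for its random part and may hold any fixed effects. The SAP never calls its reference intercept-only. It states a moderation hypothesis, calls the aim a test of interaction and names an interaction term, all of which fit a comparison that adds only the product. A reader might infer from the wording that an intercept-only reference was certainly used. The documents do not support that: it is the most natural reading of a model named without covariates, but not the only one. The sentence on the purpose of the imaging says what was to be tested, not which terms were in the reference, so it does not settle the matter either way.

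Two limits on the harm also stand. A reference that already holds treatment removes the problem of the uniform treatment effect and leaves only a possible DVR main effect. A product-only model is misled by a uniform effect only if DVR is uncentred, and the SAP is silent on centring.

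It can also be said that the SAP is written in the past tense, so that this is a request for clearer reporting. That is true if the reference held both main effects. If it did not, the test itself does not answer the stated question, and a sentence of explanation would not repair it.

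**Conclusion.** The concern holds in conditional form. The SAP does not place the treatment and DVR main effects in the reference model, and on the most natural reading the comparison does not isolate the interaction. A uniform treatment effect or a DVR main effect could then be reported as PET dependence. Whether this happened depends on a specification that the documents omit.

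A reader might go further and conclude that the association with thalamic binding is spurious. The documents do not support that: they show neither the fitted models nor any result. Nor are the 45% and 85% estimates for this trial; they rest wholly on the assumed n, effect size, ICC, DVR spread and test. What does not depend on those values is the direction: under an intercept-only reference with the three-term model, or the uncentred product alone, the rate of false PET dependence rises with the uniform treatment effect. With both main effects in the reference it does not. The point should be fixed, because one of the SAP's two stated claims depends on it and the remedy is cheap.

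**What to change.** State the fixed effects of both models. Put treatment, DVR and a participant random intercept in each, with the same period or sequence terms in both if any are used. Add only DVR x treatment to the larger model. Base the moderation claim on that 1-df term, with a small-sample t or F test and a confidence interval.

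For complete pairs there is a simple equivalent. Subtracting the two change scores cancels u and b2, so the participant's flumazenil-minus-saline change can be regressed on DVR, with a sequence indicator added if the mixed model has a period term. The slope equals the mixed-model interaction coefficient. The standard error agrees when the estimated random-intercept variance is positive. At n = 20 and ICC 0.2 that estimate is zero in about 20% of simulated data sets, and the mixed-model standard error is then smaller.

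The cost is one refit on data already collected, a possibly less favourable p-value and some power. For a DVR slope present only under flumazenil (assumed correlation 0.5 with the within-person difference, no mean effect, n = 20), the 1-df t-test has 64% power against 71% for the recalibrated three-term comparison, which also counts the DVR main effect. If the fitted reference already held both main effects, the SAP should say so; no refit is then needed.

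### The PET-by-treatment mixed model pools change scores from both crossover days, but no period (day) term is described for it, although the SAP's ANOVA in effect adjusts for day

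*SAP*

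**What the plan says.** The SAP's second paragraph describes a two-sequence, two-day crossover, "with sequence A participants receiving FMZ infusion on the first visit and sequence B participants receiving saline infusion (placebo) on the first visit". It continues: "The other treatment was given on the subsequent day for participants in both sequences". PIGD is scored before and after infusion on each day, so each participant contributes two change scores. On allocation it says "Study participants were pseudo-randomly assigned into A and B sequences". It also gives the purpose of the imaging: "FMZ PET imaging was done to collect data for the test of interaction between treatment and GABA-A receptor availability".

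The third paragraph gives the analyses. The repeated measures ANOVA of treatment by time is fitted "with additional three-way interaction term between treatment, time of administration, and sequence (A vs B) included to account for potential confounding effect of sequence". For the PET question, "a mixed linear model comparison was conducted between the random intercept model and FMZ PET by treatment interaction model". Bilaterally averaged thalamic DVR "by treatment (FMZ pharmacological therapy injection vs placebo) was used for the interaction term", and the post-minus-pre differences in PIGD score around the "infusion were used as a response variable for that model".

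No period, day, visit or sequence term is named for either mixed model, and the fixed effects of the two models are not listed. The Protocol Synopsis gives no model terms.

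**The concern.** Because the interaction is with flumazenil versus placebo, change scores from both days enter the PET model. Each participant's flumazenil-minus-placebo contrast is also a day contrast: day 1 minus day 2 in sequence A, and day 2 minus day 1 in sequence B. A shift that moves pre and post scores equally on one day cancels in the change score. A difference between days in the pre-post change itself does not cancel. Practice or familiarity with the infusion visit could produce one.

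Without a period term, such a difference becomes residual error in the DVR × treatment test, and power falls. If mean DVR also differs between the sequences, part of the day effect is attributed to DVR and the slope is biased. This is the test for which the imaging was done, and the Protocol Synopsis makes the relation between crossover response and thalamic binding part of the overarching goal. The SAP makes the adjustment in one analysis and does not describe it for the other.

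**Working it through.** **Inputs.** The design, response and interaction term come from the SAP's second and third paragraphs. The documents give no sample size, SD, day effect, DVR distribution or significance level, so there is no stated figure to reproduce. Everything numerical below is assumed: equal sequences, two-sided 5% level, normal errors.

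**Step 1: does the ANOVA term adjust for day?** Code sequence A = +½, B = −½; flumazenil = +½, placebo = −½; day 1 = +½, day 2 = −½.

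| Sequence | Day | Sequence code | Treatment code | 2 × sequence × treatment | Day code |
|---|---|---|---|---|---|
| A | 1 | +½ | +½ | +½ | +½ |
| A | 2 | +½ | −½ | −½ | −½ |
| B | 1 | −½ | −½ | +½ | +½ |
| B | 2 | −½ | +½ | −½ | −½ |

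The last two columns agree in every row. Multiplying both by time shows that treatment × time × sequence equals day × time, which is the day effect on pre-post change. With this sum-to-zero coding the ANOVA carries the adjustment that the PET model lacks.

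**Step 2: reduce the PET test to a regression.** With two change scores per person, and with treatment and DVR main effects in both models, testing DVR × treatment is the same as testing the slope in

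D = constant + β·DVR + p·s + e,

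where D is the flumazenil change minus the placebo change, s = −1 in sequence A and +1 in B, and e has SD 1. DVR is in SD units. Then p is the day-2-minus-day-1 difference in change, in residual SDs of D, and β = r/√(1 − r²) for correlation r. For r = 0.5, β = 0.5/√0.75 = 0.577. Period in the mixed model corresponds to s here.

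**Step 3: power.** If s is omitted and DVR is unrelated to sequence, the residual variance rises from 1 to 1 + p². The standard error is multiplied by √1.25 = 1.12 at p = 0.5 and √2 = 1.41 at p = 1. Including s costs one degree of freedom (N − 3 instead of N − 2). Simulated power, to within about one percentage point:

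| N | r | With period | Without, p = 0 | p = 0.25 | p = 0.5 | p = 1 |
|---|---|---|---|---|---|---|
| 10 | 0.5 | 29% | 33% | 31% | 27% | 18% |
| 20 | 0.5 | 62% | 64% | 62% | 55% | 37% |
| 30 | 0.5 | 81% | 83% | 81% | 74% | 54% |
| 20 | 0.3 | 24% | 25% | 24% | 21% | 15% |
| 20 | 0.7 | 95% | 96% | 95% | 92% | 77% |

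At r = 0.5, break-even is at p of about 0.4 for N = 10 and 0.25 for N = 20.

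**Step 4: type I error and bias.** With DVR unrelated to sequence, type I error is 4.9–5.2% with or without period. If mean DVR differs by g SD between equal sequences, the slope bias without period is approximately

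p × N(g/2) / [(N − 1) + N(g/2)²].

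For N = 20 and g = 0.5 this is p × 5/20.25 = 0.247p, that is 0.06, 0.12 and 0.25 at p = 0.25, 0.5 and 1. Simulated type I error is then 5.6%, 7.3% and 11.5%. With period it is 5%, with no bias.

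**Step 5: which models are compared?** Step 2 assumed main effects in both models. If the base model is literally a random intercept alone, the comparison adds treatment, DVR and their interaction together, on 3 degrees of freedom. With no DVR effect at all, a treatment effect of 0.5 SD of change and within-person correlation 0.5, that joint likelihood ratio test rejects about 43% of the time at N = 20, so it would not isolate the hypothesis.

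A 1-df chi-square likelihood ratio is also too liberal in small samples. Its type I error without/with period is 9.1/11.6% at N = 10, 6.6/7.5% at N = 20 and 6.1/6.5% at N = 30. The F test holds 5%.

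**The case against.** The SAP is a short narrative that lists no full set of fixed effects. It does not name treatment or DVR main effects for the mixed model either, so silence about period shows only that the term is unspecified. This stands: a period term may have been fitted and not reported, and the finding concerns the model as described.

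The documents also give no evidence of a day effect on change. Within-day differencing removes any shift common to pre and post. Adding period loses a little power when there is no day effect, and the large losses need a day effect of a full SD, which would itself be detected about 99% of the time at N = 20. This also stands, and it is why the gain is conditional. Bias needs both a day effect and a DVR imbalance between sequences, and neither is documented; pseudo-random assignment is not evidence of imbalance.

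Finally, the ANOVA text speaks of sequence, not day, and the equivalence depends on sum-to-zero coding. That is a fair wording point, but the term has that meaning in this design.

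None of this removes the gap. A reader who fits the two models as named gets a comparison that leaves any day effect in the error and, if the base is intercept-only, does not isolate DVR × treatment.

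**Conclusion.** The concern holds as a cheap improvement; it is not a demonstrated error in the results. As described, the PET test has no period term, and the two models compared are not stated closely enough to show that they differ only by DVR × treatment. The main cost is power, and only if pre-post change differs between days: at N = 20 and correlation 0.5, about 7 points (62% − 55%) for a half-SD day effect and about 25 points (62% − 37%) for a one-SD effect. For a small or absent day effect, including period gains nothing or loses slightly. Type I error is at risk from the omission only if DVR also differs between sequences.

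All these figures rest on assumed N, correlation and day effect, equal sequences, and treatment and DVR main effects in both models. They do not apply if the base model contains only the random intercept.

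**What to change.** State both models in full. Base: random intercept, treatment, DVR and period (day 1 or day 2). Full: the same plus DVR × treatment. Test the added term with a t or F statistic on small-sample degrees of freedom, not a chi-square likelihood ratio. Report the number of participants and mean DVR in each sequence. If period was already in the fitted model, say so.

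The SAP is written in the past tense. The result should therefore be shown beside the model as described, and marked as added later if the data had been seen. The ANOVA needs no change, though calling its three-way term a day effect would be clearer.

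The cost is one sentence in the SAP, one re-fit on data already collected and one degree of freedom. With no day effect and correlation 0.5, power falls from 33% to 29% at N = 10, from 64% to 62% at N = 20 and from 83% to 81% at N = 30.
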